be protected by use of subject code on all data and questionnaires. Data including subject identifiable information will be linked to a code on RedCap for this study for access and only research staff will have access. An exception to this rule is the clinic provider and site staff who work directly with the women onsite.

Program Team

The Lab Manager and Lab Coordinator will help the PI ([name]) in organizing all aspects of the study. These individuals will be current or former students from the Department of Psychological Science's Postbaccalaureate Program. They will be responsible for tracking recruitment, scheduling research assistants, and ensuring that the site is well-stocked with necessary supplies. Weekly, the Lab Manager and Lab Coordinator will meet with [name] to review all aspects of the study, troubleshoot any problems, and create schedule for the other Research Assistants (RAs). The RAs will be highly trained Postbaccalaureate, graduate, or undergraduate students from the University of California, Irvine.

Safety of Program Staff

While we believe that conducting this study is highly important for public health, it is critical that the program staff prioritize their own safety first. If you feel that you are in danger (physically, emotionally, psychologically) in any way, end the study activities and inform the research coordinator or the PI as soon as you can safely do so. This is particularly important during COVID-19. Please report any lapses in COVID-19 protocol to [name] and the Leadership team immediately. If there is any chance you have been exposed, it is imperative *that you do not come to site*. The study leadership ([name] and the Lab Manager / Lab Coordinator)

Subsection 2.2 - Phase II Scope of Work & Participant Flow Diagram

1. General Recruitment

- a. We will recruit 5 cohorts of women from the two sites by research staff via flyers and announcements during site programming. Due to COVID-19, this strategy may change as the situation evolves.
- b. Participants will then be given an eligibility screener via tablet with either [name] or the Lab Manager/Lab Coordinator available to answer any questions.
 - i. A key inclusion criteria is subthreshold current PTSD. Thus, the women will be given a PTSD screener for the trauma that is bothering them most right now. There may be multiple traumas the women have experienced they should be prompted to pick the one that is most troubling to them at the time of screener completion.

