Participants have the right to refuse the collection of urine or saliva and it is important to understand that an individual may want to refuse due to the following:

Step 1: Assess reasons why participant does not want to have their sample collected.

- May experience concern that their friends, acquaintances, or shelter staff will be informed of the results of their surveys or urine.
- Other possible reasons?

In the event a participant refuses the sample collection, inquire about the following:

Step 2: Respond to their reasons why they do not want to give urine or saliva samples.

We encourage our participants to complete as many of the procedures as they are comfortable with. Please offer to have [name] or Lab Management answer any questions the participant may have regarding the measures. However, participation is completely voluntary, and the participant may skip any aspect of the procedure that they chose without penalty and still be in the study.

Subsection 2.16 - Phase II Dealing with Intervention Program Attrition

Attrition is conservatively estimated at 10% for first follow-up and 20% for 6 month follow-up. To account for an estimated 30% of women to be screened with subthreshold or threshold PTSD, 448 women will be screened, approximately 134 enrolled, with approximately 120 for immediate post-intervention assessment and 96 at 6-month follow-up. This may change due to COVID-19, but we will work hard to ensure retention of participants during the study. The Locator Guide is key to maintaining effective follow-up.

• Completion of the intervention program is defined by completing at least 6 out of the 9 classes. We will keep track of the number of classes using the adherence tracker on REDCap. Make-up classes will be offered to women who can not make the class,

particularly as it pertains to COVID-19 or other obligations the women have such as court appearances.

• The minimum amount of time required for the regimen is 8 weeks and the maximum is 10 weeks.

Subsection 2.17 - Phase II Follow-Up Focus Groups

At six-month follow-up, we will contact the women with assistance from the site supervisor or by using our Locator Guide (see Appendix). Research Staff will travel to the participant's location, as they may not be available to return to site due to COVID-19 restrictions or other factors. If participant moved out of state, the follow-ups may be conducted over Zoom or phone.

Subsection 2.18 - Phase II Compensation

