- Trained in the California Mandatory Reporting Laws governing reporting of child abuse, domestic violence, and elder/dependent abuse. Protocols governing reports to the California Department of Family and Child Protective Services, or (in the case of domestic violence) local police, will be carefully followed. Study participants will receive full disclosure regarding mandatory reporting laws during the informed consent process and discussion of confidentiality. In terms of current or recent abuse experience, research staff will refer the participants to the onsite Prototypes clinical staff.

During research study training, Research Staff will be evaluated using the competency grid and mock session review. Research Staff will also complete a quiz to be reviewed with the PI prior to interacting with the participants.

Subsection 2.21 - Data Entry, Management & Confidentiality

In Phase 2, secure and encrypted platforms will be used:

- **REDCap:** Interview data will be captured electronically using REDCap (Research Electronic Data Capture; http://project-redcap.org/), a secure, web-based application designed to support data entry and storage for research studies. Participants will answer surveys via an electronic tablet and the data will be uploaded in real-time. Possible errors, including incomplete responses, logic checks, and data range checks will be flagged by the RedCap software during input so that they can be corrected immediately. Laboratory data will be entered in REDCap electronic forms.
- [name] will routinely check to ensure data is accurately entered. The Data Safety and Monitoring Board (DSMB) will also meet after the enrollment of every 30 participants to review/

Procedures to safeguard confidentiality

Confidentiality of data will be protected by use of subject code on all data and questionnaires. Any forms that link participant with their codes will be stored electronically on UCI's secure server and only senior research staff and the PI will have access. All self-report data will be immediately uploaded onto UCI's secure server via RedCAP. Saliva samples will use the subject code number and will not be labeled with the participant's name.

- Participants will be reminded that their interview questions will be provided over a tablet that will immediately transfer the data to the UCI secure server and site staff will not see their data.

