- We will minimize the risk by strictly adhering to confidentiality procedures. All study staff will be rigorously trained in methods to promote confidentiality. The staff will also be taught to treat participants in a non-judgmental, professional and confidential manner.
- A Data Safety and Monitoring Board will be put in place for monitoring of the data collected.
- Confidentiality of data will be protected by use of subject code on all data and questionnaires. Data including subject identifiable information (eg: locator form etc) will be linked to a code on REDCap for access in real time to track participants and only research staff will have access. REDCap also allows for participant's names and IDs to be viewed without access to their responses to the other items in the survey. Tracking of participants for their follow-ups will be based upon the information the participant reveals on their Locator Guide. When contacting people over the phone, we will use their preferred method and the research staff will identify themselves per participants' wishes.
- To protect confidentiality and reassure subjects, the research staff will be providing explicit explanations in the beginning of the program that they will share no confidential information. The trained research staff will administer the questionnaires individually to the participants.
- Subject identifiable data will be destroyed upon completion of the study. All the data will be stripped off any identifiable information and only de-identified database will be kept for analysis and dissemination.

Subsection 2.22 – Using REDCap

- For electronic data entry, log onto RedCap (https://redcap.med.upenn.edu/) with your user ID and password.
- RedCap also incorporates suitable validity checks at the point of data entry to prevent "out of range," "missing" or other checkable data entry errors.

Subsection 2.23 - Data Security

- All CRFs and questionnaires must be identified by a code number (Study ID) only and patient identifier information will also be linked on REDCap through this code.
- The informed consent with the participants' names and signature will be on REDCap and a digital copy should be printed out of REDCap and stored in a local hard drive not connected to server.
- All databases are accessible only to key investigators and senior leadership of the project.
- The electronic data files are stored on the secure, password-protected UCI Health Science server.

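### Section 2.1 exempts site staff, without limit, from the rule on who may see identifiable study data, while Section 2.21 has participants assured of the opposite

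*Combined protocol and SAP*

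**What the plan says.** Under its heading on confidentiality and ethical issues, Section 2.1 sets the rule: "Data including subject identifiable information will be linked to a code on RedCap for this study for access and only research staff will have access". The next sentence reads: "An exception to this rule is the clinic provider and site staff who work directly with the women onsite". Nothing there narrows the exception by type of data, purpose or permission. The protocol is printed twice in the file and both copies carry the same text, so this is not a fault of extraction.

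Section 2.21 (procedures to safeguard confidentiality) has participants reminded that the tablet will "immediately transfer the data to the UCI secure server and site staff will not see their data". The same section has research staff explain at the start of the program that "they will share no confidential information". Section 2.23 states: "All databases are accessible only to key investigators and senior leadership of the project".

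Two other parts of the plan bear on these statements. Section 2.20 says: "Study participants will receive full disclosure regarding mandatory reporting laws during the informed consent process". Section 2.15, on refusal of urine or saliva, gives as its example of a participant's reason: "May experience concern that their friends, acquaintances, or shelter staff will be informed of the results of their surveys or urine".

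**The concern.** The women live in the residential drug-treatment facilities whose staff Section 2.1 exempts. The study collects drug use, trauma history and psychiatric symptoms from them, and its suicide-risk procedure has staff record suicidality. Two staff members reading different sections could reach opposite conclusions about whether a counselor may look at a resident's record, and the participant is told only one of those answers.

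The first thing at stake is whether what participants are told is true. Section 2.15 instructs the research assistant to respond when a woman gives a reason for refusing a sample. If she fears that site staff will learn her results, the plan as written gives the assistant no answer that is reliably correct.

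The second is data quality. A woman who learned of the exception, or doubted the assurance, might refuse a specimen or report fewer symptoms or less use. The documents allow this to be stated as a possibility and no more.

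**Working it through.** The documents attach no figure to this point, so there is none to reproduce. The check is a comparison of every statement on access and confidentiality.

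| Place | Who may see what | Exception for site staff |
|---|---|---|
| 2.1 | Code-linked data, including identifiable information: research staff | Yes, with no stated limit |
| 2.21, forms linking names to codes | Senior research staff and the principal investigator | None |
| 2.21, what participants are told | Site staff see none of their data | None |
| 2.21, identifiable data such as the locator form | Research staff, in nearly the same words as 2.1 | None |
| 2.23 | Databases: key investigators and project leadership | None |
| Appendix III, risk management list | Identifiers: the principal investigator, mentors and data manager | None |

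**Step 1: is there a conflict?** The exception in 2.1 qualifies a rule about data that include identifiable information, a class wide enough to take in responses. The reminder in 2.21 denies site staff any sight of a participant's data. Read as written, both cannot hold. Section 2.21 also restates the 2.1 rule without the exception, so the two sections disagree even on the rule.

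**Step 2: can a narrower reading reconcile them?** Possibly. Section 2.21 notes that REDCap can show names and IDs without responses, and Section 2.17 uses the site supervisor to help find women at six months. The exception may have been meant for identity and tracking only, but 2.1 does not say so. Even on that reading, the restrictions on identifiers in Appendix III and on the locator form in 2.21 would still need to be squared with it.

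**Step 3: the second assurance.** The statement in 2.21 that nothing confidential will be shared has no qualifier. Against it stand:
- mandatory reporting of abuse (2.20);
- the suicide red-flag procedure in Appendix III, under which staff pass what they have recorded to the treatment program counselor or an on-call clinician;
- the harm-to-others procedure in Appendix III, under which staff report to the licensed clinician at the site;
- the instruction after the stress task to tell site staff of any potential problem (2.10).

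The signed release in Appendix III concerns communication over further treatment after a suicide-risk event. The disclosures listed above are not made conditional on it.

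**Step 4: does this reach the treatment comparison?** The SAP fits group, time and group-by-time as fixed effects, with site as a fixed effect. Suppose reporting at wave *t* is shifted by *b(t)*, the same in both arms, on the scale of the model. With *M* and *H* the mean outcomes in the MBSR and HP arms, the contrast between arms in change from T1 is

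[(M(t) + b(t)) − (M(1) + b(1))] − [(H(t) + b(t)) − (H(1) + b(1))] = [M(t) − M(1)] − [H(t) − H(1)].

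The shift cancels. The exception in 2.1 covers both arms and both sites, so it does not by itself bias this contrast. A reporting difference between sites that changed over time would not be modelled, because the SAP has no site-by-time term. Nothing in the documents indicates that the sites would handle access differently.

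**The case against.** The strongest reply is that this is loose drafting in a staff manual, with no sign of any working route to the data. Site staff cannot avoid knowing who takes part: they announce the study, receive women after the stress task and help to locate them later. No passage gives them REDCap rights or urine results. Answers are not stored on the tablets and go straight to the university server (2.4, 2.21), and the research assistant reads the urine cup (2.10). Women are told that site staff will not have access, so a sentence they never see would not change their answers. Section 2.20 already requires mandatory reporting to be explained at consent, so the unqualified promise in 2.21 is not all they hear.

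Most of this stands. It disposes of a stronger inference that a reader might draw: that self-report in this trial is biased, or that disclosure to site staff is built into the procedure. The documents show neither. The wording permits access; it does not show that access occurs.

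A reader might also try to put a number on false changes in reported drug use between the on-site and later assessments. The documents give no rates of under-reporting, and Section 2.14 keeps follow-ups on site unless a woman has moved, so a clean change of setting between waves cannot be assumed. A positive urine test counts as positive whatever the self-report (2.11), which is a partial check. It covers five drug panels, and the specimen can be refused. The PCL-5 and PROMIS depression scores have no such check. Nor does the adverse-event list help the stronger reading: its disclosure item concerns immigration status, a different matter.

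The reply does not remove the conflict itself. An intended narrow meaning that is not written down does not make the assurance safe to give, and disclosure of reporting laws at consent does not cover access by site staff.

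**Conclusion.** The concern holds as a conflict between stated rules that should be resolved. Section 2.1 lets site staff past the access rule without limit; 2.21, 2.23 and Appendix III do not. If 2.1 is followed, what residents are told is untrue on the very worry that 2.15 anticipates. The promise in 2.21 to share nothing confidential is also wider than the plan can honor.

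The assurance goes to every participant, about 134 planned (2.16), in both arms. The effect on the data has no known size. Refusal or under-reporting could follow if the exception is used or becomes known, but the documents do not establish that either happens, and no bias between arms is shown.

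The conclusion rests on the text as printed. It does not depend on which meaning of the exception was intended, because either meaning requires an edit. The consent pages were not available, so whether their wording agrees with 2.1 or with 2.21 could not be checked.

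**What to change.** 1. In Section 2.1, limit the exception to the participation and contact information that site staff need for scheduling and tracking.
2. State one rule in 2.1, 2.21 and 2.23: site staff have no access to questionnaire responses or urine results, except through the mandatory-reporting and red-flag or distress disclosures the plan already describes. Those procedures are not altered. Bring the identifier statement in Appendix III into line.
3. Qualify the promise in 2.21 so that it names the same exceptions, and give research assistants that wording for the refusal conversation in 2.15.
4. Check that both consent versions agree with the rule, and confirm that REDCap permissions follow it.

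The cost is a few sentences, a check of the consent wording and a permissions review. Some women may disclose slightly less once the exceptions are stated plainly, but Section 2.20 already requires the reporting laws to be explained at consent.
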